Recruitment and enrollment into the study will occur on an ongoing basis, with each group being recruited and vaccinated in sequence.

48 subjects will be enrolled into 4 groups of 12:

[figure not shown]
Subjects will be enrolled sequentially and upon enrollment will be randomized to one of the following IP assignments in a double-blind fashion:

- Group 1 IP allocation (n=12 subjects):
  - 12 subjects will receive 100 $\mu$ g Na-GST-1/Alhydrogel® delivered by IM injection in the deltoid muscle.
- Group 2 IP allocation (n=12):
  - 12 subjects will receive Na-GST-1/Alhydrogel® plus 500 $\mu$ g CpG 10104 delivered by IM injection in the deltoid muscle.
- Group 3 IP allocation (n=12):

- 12 subjects will receive Na-GST-1/Alhydrogel® plus 5µg AP 10-701 delivered by IM injection in the deltoid muscle.
- Group 4 IP allocation (n=12):
  - 12 subjects will receive sterile saline delivered by IM injection in the deltoid muscle

**Estimated Time to Complete Enrollment:** 6 months

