Secondary Objective #3: To assess the duration of antibody responses to Na-GST-1 induced by vaccination with Na-GST-1/Alhydrogel® delivered with or without AP 10-701 or CpG 10104.

*Secondary Outcome #2 and #3 Measures:*

The following parameters will be evaluated for each formulation of Na-GST-1, in comparison to the saline placebo control:

1. The anti-Na-GST-1 IgG antibody response, by a qualified indirect enzyme-linked immunosorbent assay (ELISA) at approximately 14 days after each vaccination, and approximately 1, 2, 4, 6, 7, 8 and 10 months after the third dose.

*Analysis Plan:*

- a. The proportion of participants with detectable anti-Na-GST-1 IgG responses will be summarized as a descriptive measure.
- b. IgG levels will be displayed graphically by study group using notched box plots at each time point.
- c. Geometric mean antibody responses will be compared between vaccine formulation groups at each time point. Comparisons between groups will be made by a one-way analysis of variance (ANOVA) with pair-wise comparisons between groups made by contrasts.
- d. Geometric mean antibody responses for each antigen will be compared using a regression model with main effects for the doses of Na-GST-1 (0 or 100µg), AP 10-701 (0 or 5 µg), and CpG 10104 (0 or 500µg).
- e. For antigen-specific log IgG levels, a three-way ANOVA will be conducted, with Na-GST-1, CpG 10104 and AP 10-701 doses as factors.
- f. Pair-wise comparisons of IgG levels on study Day 126 (2 weeks after the third vaccination) across all combinations of Na-GST-1 doses (i.e., 0 [placebo] or 100 µg), AP 10-701 doses (i.e., 0 or 5 µg), and CpG 10104 doses (0 or 500µg) will be assessed using Tukey's HSD.
- g. Percent change in IgG antibody levels from days of vaccination to days 7, 14 and 28 post-vaccination will be compared between vaccine formulation and dose groups. Values will be reported with 95% confidence intervals.
- h. Percent change in IgG antibody levels from vaccination day #1 to #2, from vaccination day #2 to #3, and from vaccination day #3 to day of CHHI will be compared between vaccine formulation and dose groups to assess the sustainability of the response from trough to trough and post-CHHI. Values will be reported with 95% confidence intervals.
- i. Percent change in IgG antibody levels from the peak following the third vaccination, to 1, 2, 4, 6, 7, 8 and 10 after the third vaccination. Values will be reported with 95% confidence intervals.

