- j. Percent change in IgG antibody levels from the day of CHHI to 1, 3, 5, 6, 7 and 9 months post-CHHI. Values will be reported with 95% confidence intervals.
- k. A longitudinal model will be built to describe the IgG levels over time. Using a longitudinal panel model, differences in antibody isotype levels by formulation of Na-GST-1 will be explored. This will be accomplished using Proc Mixed in SAS 9.3 so the analysis will take account of the correlation between measurements on the same subject.
- l. Logistic regression will be explored for the binary response of hookworm infection post-CHHI as a function of antibody response, and a Poisson regression of the event counts (i.e., infection) as a function of IgG antibody response. In these models, vaccination group will be a covariate, rather than just using the IgG responses.

**Exploratory Objective #1:** To assess the relationship between the functional capacity of vaccine-induced antibodies that neutralize the *in vitro* activity of native Na-GST-1 enzyme and responses to CHHI in healthy, hookworm-naïve adults.

*Exploratory Outcome #1 Measure:*

The following parameters will be evaluated for each formulation of Na-GST-1, in comparison to the saline placebo control:

1. The functional capacity of vaccine-induced antibodies to neutralize the *in vitro* activity of the native Na-GST-1 enzyme.

*Analysis Plan:*

- a. Percent inhibition of native enzyme activity will be displayed graphically for the various study groups at each time point.
- b. Three-way ANOVAs with Na-GST-1, CpG 10104, and AP 10-701 as factors and percent inhibition as the outcome will be estimated.
- c. A longitudinal model will be built to describe percent inhibition of native enzyme activity over time. Using a longitudinal panel model, differences in percent inhibition by formulation of Na-GST-1 will be explored. This will be accomplished using Proc Mixed in SAS 9.3, so the analysis will take account of the correlation between measurements on the same subject.

**Exploratory Objective #2:** To compare the impact of vaccination with Na-GST-1/Alhydrogel® delivered with or without AP 10-701 or CpG 10104 on levels of hookworm DNA as detected by real-time PCR in healthy, hookworm-naïve adults challenged with CHHI.

*Exploratory Outcome #2 Measure:*

The following parameters will be evaluated for each formulation of Na-GST-1, in comparison to the saline placebo control:

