### **2.2 Study Design**

The study will be a randomized, double blind, placebo-controlled Phase 2 clinical trial in healthy hookworm-naïve adult subjects. This study is designed to evaluate the efficacy, safety, reactogenicity, and immunogenicity of *Na*-GST-1/Alhydrogel® administered with or without the point-of-injection addition of the immunostimulants AP 10-701 or CpG 10104. To assess the impact of vaccination with these different vaccine formulations on infection, subjects will be challenged with 50 infectious *N. americanus* larvae by controlled human hookworm infection (CHHI) 4 weeks after the 3rd vaccination. Safety parameters will be monitored throughout the study.

Subjects will be invited to participate in the study by means of verbal and email announcements and poster, newspaper, and online advertisements. After providing written informed consent, subjects will undergo eligibility screening, including a complete medical history; physical examination; hematology testing; liver and renal function testing; anti-double stranded DNA (anti-dsDNA) and rheumatoid factor (Rf) testing; Human Immunodeficiency Virus (HIV), Hepatitis B, and C testing; fecal occult blood testing; fecal examination for ova and parasites; and, urinalysis (for protein and glucose). Urine pregnancy testing will be performed on all female subjects. All clinically significant abnormalities will be reviewed with subjects and they will be referred for follow-up care if appropriate. After screening, those subjects determined to be eligible, based on the inclusion and exclusion criteria described in Section 5 in the study protocol, will be invited to participate in the study. No exemptions from the inclusion or exclusion criteria will be granted on inclusion/exclusion.

In the study, 48 subjects will be enrolled and randomized into 4 groups. Groups will not be enrolled separately; rather, eligible subjects will be randomly assigned to a group upon enrollment in a double-blind fashion (i.e., neither the subject nor the investigators will know to which group the subject has been assigned). In the first group (n=12), subjects will receive 100µg *Na*-GST-1/Alhydrogel®. In the second group (n=12), subjects will receive 100µg *Na*-GST-1/Alhydrogel® co-administered with 500µg CpG 10104. In the third group (n=12), subjects will receive 100µg *Na*-GST-1/Alhydrogel® co-administered with 5µg AP 10-701. In the fourth group (n=12), subjects will receive sterile saline placebo.

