#### 5.7.4.2 Secondary Endpoint Analysis

Fecal egg counts of the subjects in each of the vaccination (Groups 1, 2 and 3) and placebo (Group 4) groups will be assessed for normality. If normality assumption is confirmed, the comparison between vaccination groups (Group 1, 2 and 3) and placebo group (Group 4) will be done using T-test. Otherwise, the vaccination groups (Group 1, 2 and 3) will be compared with the placebo group (Group 4) using a Wilcoxon-Mann-Whitney rank-sum test. Continuous data will be summarized using the descriptive statistics (mean, median, minimum, maximum and median 95% CI). Mean or Median differences and corresponding 95% CIs will be computed for each pairwise comparison.

Time to patent infection (i.e., the first timepoint at which hookworm eggs are detectable in a fecal sample) will be displayed using Kaplan-Meier estimates, with log-rank tests used to compare the distribution of time-to-patency between groups and censoring of early withdrawals or those failing to develop patent infection.

The detectable anti-*Na-GST-1* IgG responses will be summarized as a descriptive measure using descriptive statistics (mean, standard deviation, median, minimum and maximum) for each observed measurement by vaccination groups and placebo. IgG levels will be displayed graphically by study group using time series and notched box plots at each time points.

Geometric mean antibody responses will be compared between vaccination groups and placebo at each time point using an ANOVA model. An ANOVA model will be fitted with IgG responses as the dependent variable and vaccination groups and placebo as independent variables. The estimated geometric least square means and geometric least square means difference from the model, 2-sided *p*-value and 95% CI for vaccination groups compared to placebo group will be constructed and presented for each time point.

Percent change in IgG antibody levels from days of vaccination to days 7, 14 and 28 post-vaccination, as well as percent change in IgG antibody levels from the peak following the third vaccination to 1, 2, 4, 6, 7, 8, and 10 months post-vaccination will be summarized using descriptive statistics (mean, standard deviation, median, minimum, maximum and 95% CI) for each observed measurement along with the percent change from baseline.

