#### **7. CHANGES OF ANALYSIS FROM PROTOCOL**

The analysis point no. 2 in the analysis plan section secondary outcome #2 and #3 measures performs the ANOVA. Hence analysis Section “e” (Protocol Version 4.0 Page no.72) is not required if it is not specific to three-way ANOVA.

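### SAP Section 7 drops the protocol's three-way ANOVA only on a condition that is not met, and with 4 of the 8 factor combinations present that model is either non-estimable or redundant

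*SAP*

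**What the plan says.** Protocol 11.4, under Secondary Outcome #2 and #3 Measures, lists three overlapping models for IgG:

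- Item c: "Comparisons between groups will be made by a one-way analysis of variance (ANOVA) with pair-wise comparisons between groups made by contrasts".
- Item d: a "regression model with main effects for the doses of Na-GST-1", AP 10-701 and CpG 10104.
- Item e: "For antigen-specific log IgG levels, a three-way ANOVA will be conducted, with Na-GST-1, CpG 10104 and AP 10-701 doses as factors".

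The three-factor form returns in the exploratory analyses. For neutralization, item b reads "Three-way ANOVAs with Na-GST-1, CpG 10104, and AP 10-701 as factors and percent inhibition as the outcome will be estimated". Item b for affinity has the same form.

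SAP Section 7 is the SAP's list of changes from protocol, and it has one entry. It argues that an ANOVA is already being done and that item e therefore "is not required if it is not specific to three-way ANOVA". It mentions neither exploratory three-way ANOVA.

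SAP 5.7.4.2 fits IgG with a single factor, group. It reports "The estimated geometric least square means and geometric least square means difference from the model" for the vaccination groups compared with placebo.

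The design is stated plainly: "48 subjects will be enrolled into 4 groups of 12". Group 1 receives antigen on Alhydrogel, Group 2 the same "co-administered with 500µg CpG 10104", Group 3 the same with AP 10-701, and Group 4 saline.

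**The concern.** The entry in Section 7 does not settle what will be run. Its condition is that item e is not specific to a three-way ANOVA, but item e is one. By the letter it is retained; by the apparent intent, and by 5.7.4.2, it is dropped. Two programmers following the same SAP could deliver different analyses.

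The doubt matters because the model does not suit the design. No arm receives an immunostimulant without antigen, and no arm receives both. A factorial model therefore either asks for effects the data cannot supply or relabels the group comparison under factor names that invite misreading. The neutralization and affinity analyses inherit the same problem.

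A related gap appears if item e is simply deleted. Hypothesis 2 (Protocol 11.1; SAP 5.1) is that adding AP 10-701 or CpG 10104 raises IgG over antigen on Alhydrogel alone. The SAP's ANOVA names only comparisons with placebo, so it would not contain that contrast.

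**Working it through.** The plan gives no figure for this analysis, so there is none to reproduce. The check is of the design matrix.

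**Inputs.** Arms from the Protocol Summary and SAP 2.2, 12 subjects each. Code N, C and A as 1 if antigen, CpG or AP is given.

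| Group | Int | N | C | A | N×C | N×A | C×A | N×C×A |
|---|---|---|---|---|---|---|---|---|
| 4 (saline) | 1 | 0 | 0 | 0 | 0 | 0 | 0 | 0 |
| 1 | 1 | 1 | 0 | 0 | 0 | 0 | 0 | 0 |
| 2 | 1 | 1 | 1 | 0 | 1 | 0 | 0 | 0 |
| 3 | 1 | 1 | 0 | 1 | 0 | 1 | 0 | 0 |

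Absent are CpG alone, AP alone, CpG with AP without antigen, and all three together.

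**If item e includes interactions.** N×C equals C, N×A equals A, and C×A and N×C×A are all zero. Eight columns reduce to rank 4. None of the four interactions is estimable. In that model the three averaged main effects and all six least-squares factor means are not estimable either.

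**If item e is main effects only.** Let m1 to m4 be the group means on the log scale. Solving the four equations gives:

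- intercept = m4
- antigen = m1 − m4
- CpG = m2 − m1
- AP = m3 − m1

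Four parameters fit four means exactly, leaving 48 − 4 = 44 residual degrees of freedom, as in the one-way ANOVA. In simulated data both fits had the same residual sum of squares (34.693). Item e is then item d again, and both are item c relabelled.

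**Factor means, if any were reported.** Equal-weight least-squares means from the main-effects model are:

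| Factor level | Formula | Combinations absent |
|---|---|---|
| Antigen 0 | m4 − m1 + ½m2 + ½m3 | 3 of 4 |
| Antigen 100 µg | ½m2 + ½m3 | 1 of 4 |
| CpG 500 µg | ½m4 − m1 + m2 + ½m3 | 3 of 4 |
| AP 5 µg | ½m4 − m1 + ½m2 + m3 | 3 of 4 |

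The antigen 100 µg mean gives no weight to Group 1, the arm that received antigen without an immunostimulant.

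**Illustration under assumed values.** The documents give no geometric means in the text. Writing GM for the geometric mean of a group, the ratio of factor mean to actual arm is √(GM4·GM3)/GM1 for CpG, √(GM4·GM2)/GM1 for AP, and √(GM2·GM3)/GM1 for antigen 0.

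- Assume saline 10, Group 1 1,000, Group 2 5,000, Group 3 3,000. CpG: √30,000/1,000 = 0.173, so 866 against 5,000 (5.8-fold low). AP: √50,000/1,000 = 0.224, so 671 against 3,000 (4.5-fold low). Antigen 0: √15,000,000/1,000 = 3.87, so 38.7 against 10 (3.9-fold high).
- Same, but saline 100. CpG: √300,000/1,000 = 0.548 (1.8-fold low). AP: √500,000/1,000 = 0.707 (1.4-fold low). Antigen 0: unchanged at 3.9-fold high.
- Saline 10 and all vaccine arms 1,000. CpG and AP: √10,000/1,000 = 0.1 (10-fold low). Antigen 0: √1,000,000/1,000 = 1 (no error).

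**Coverage of hypothesis 2.** It needs m2 − m1 and m3 − m1. The ANOVA in SAP 5.7.4.2 names m1 − m4, m2 − m4 and m3 − m4.

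**The case against.** The best reply is that Section 7 plainly means to drop item e: it says the ANOVA is already done and draws a conclusion from that. The SAP contains no three-factor model anywhere. On that view the defect is one muddled clause. That is a fair reading of intent, but a change-from-protocol entry has to state what changes, and this one states a condition that its own subject fails. It also leaves the two exploratory ANOVAs untouched.

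It can also be said that item e names no interaction and that a main-effects version is fully estimable. This stands: neither document says which is meant, so non-estimability is conditional. But the main-effects version already exists as item d, so item e then adds nothing.

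Item c of the protocol already provides pairwise contrasts. That also stands, and it means the adjuvant comparison is missing from the SAP's ANOVA, not from the protocol.

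Three stronger readings are tempting and not supported.

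- A reader might infer that misleading factor means will be printed. No document promises factor means for item e. The least-squares means in SAP 5.7.4.2 belong to the one-factor group model and equal the arm means on the analysed scale. Raw marginal means would be mixtures of real arms, and for antigen 0 simply the placebo mean.
- A reader might infer that the plan yields two antigen effects: Groups 1–3 pooled versus saline under sequential sums of squares with antigen entered first, or Group 1 versus saline under partial ones. The type is unstated, but nothing proposes reporting both.
- The fold errors above might be taken as expected findings. They are arithmetic on assumed means.

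**Conclusion.** The point holds. As written, Section 7 does not remove item e, and item e is either non-estimable in its interactions (8 columns, rank 4) or a repeat of item d and the one-way model. The same defect sits in the three-way ANOVAs for neutralization and affinity, which Section 7 does not address. The ANOVA in SAP 5.7.4.2 omits the adjuvant-versus-alone comparison that hypothesis 2 requires.

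The reach is limited to secondary and exploratory immunogenicity; the infection endpoint is untouched. The structural result rests only on the four stated arms. It assumes that item e in the protocol version the SAP cites (Version 4.0) is the three-way ANOVA found in the supplied protocol, which Section 7's own mention of a three-way ANOVA supports. Any distortion of factor means arises only if equal-weight least-squares factor means are actually reported, and its size depends on unknown antibody levels.

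**What to change.** Replace the entry in SAP Section 7 with an unconditional one, for example:

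> Protocol 11.4 item e (IgG) and the three-way ANOVAs for exploratory outcomes 1 (neutralization) and 3 (affinity) are replaced by the one-way four-group model. Contrasts reported: Groups 1, 2 and 3 each minus Group 4; Group 2 minus Group 1 (CpG 10104); Group 3 minus Group 1 (AP 10-701). No interactions and no factor marginal means will be reported.

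Amend SAP 5.7.4.2 to list the same five contrasts. The two adjuvant contrasts are added to the placebo comparisons and must not displace them, because these outcomes are defined in comparison with saline. Item d may stay or be dropped as redundant. The SAP should also say whether the five contrasts are adjusted for multiplicity.

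The cost is SAP wording, best made before unblinding. It needs no new data and no change in sample size, and it gives up no estimable effect.

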#### **8. REFERENCES**

Not Applicable

#### **9. APPENDICES**

Not Applicable

## **10. TABLES, LISTINGS AND FIGURES**

The list of Tables, Listings and Figure to be prepared for this study will be provided as a separate document.

